Lenalidomide Maintenance Therapy in Multiple Myeloma: A Phase II Clinical and Biomarker Study

NCI Principal Investigator: [name].^{A-F}
Lymphoid Malignancies Branch (LYMB), CCR, NCI
National Institutes of Health
[name]
[name]
[contact]
Email: [contact]

NIH Associate Investigators: [name]., GMB, CCR, NCI^{B,E-F}
[name]., Ph.D., GMB, CCR, NCI^{B,E-F}
[name]., GMB, CCR, NCI^{B,E-F}
[name]., BDMS, OCD, CCR, NCI^{B,E-F}
[name]., Lab of Path, NCI^{B,E-F}
[name]., Ph.D., Heme Service, CC^{B,E-F}

Non NIH Associate Investigator: [name]., FDA, Volunteer^{A-F}

Referral Contact: [name].

Study Coordinator: [name], R.N., OCN^{A,B}
[contact]
Email: [contact]

Abbreviated Title: Revlimid maintenance for MM

Version Date: 01/06/2017

Investigator Roles:

- A. Obtaining information by intervening or interacting with living individuals for research purposes
- B. Obtaining identifiable private information about living individuals
- C. Obtaining the voluntary informed consent of individuals to be subjects
- D. Making decisions about subject eligibility
- E. Studying, interpreting, or analyzing identifiable private information or data/specimens for research purposes
- F. Studying, interpreting, or analyzing de-identified data or specimens for research purposes
- G. Some/all research activities performed outside NIH

Commercial Agents:

Lenalidomide

Identifying Words: Revlimid, immunomodulatory drugs, T cell activity, gene expression

Abbreviated Title: Revlimid maintenance for MM

Version Date: 01/06/2017

Précis

Background:

- Multiple myeloma (MM) remains largely an incurable disease with an estimated median survival of 6-7 years in standard risk myeloma and 2-3 years in high risk disease despite treatment with autologous stem cell transplantation (ASCT).
- Maintenance therapy to achieve sustained suppression of residual disease following chemotherapy or ASCT has long been viewed as a desirable approach for extending survival in MM.
- Giving the immunomodulatory drug lenalidomide after induction or re-induction treatment may stimulate the immune system in various ways to stop or slow the return of cancer.
- It is not yet known how immune stimulatory effects of extended dosing with lenalidomide in the maintenance setting correlate with clinical benefits.

Objective:

- Assess T cell (CD4, CD8), NKT and NK cell numbers in peripheral blood during the course of lenalidomide maintenance therapy in treated MM patients.

Eligibility:

- Patients with multiple myeloma who have achieved stable disease or better response, assessed at \geq 4 weeks after completing induction or re-induction treatment
- Age \geq 18 years
- ECOG PS of 0-2
- Adequate hematological parameters defined by: absolute neutrophil count \geq 1.0 K/uL, hemoglobin \geq 8 g/dL, and platelet count \geq 75 K/uL
- Adequate hepatic function, with bilirubin $<$ 1.5 x the ULN, and AST and ALT $<$ 3 x ULN
- Adequate renal function with creatinine clearance (CrCl) of greater than or equal to 40 mL/min. CrCl will be calculated using the Cockcroft-Gault method. If the calculated CrCl based on Cockcroft-Gault method is $<$ 40 mL/min, patient will have a 24 hr urine collection to measure CrCl. The measured CrCl must also be \geq 40 ml/min

Design:

- Single arm, single stage, phase II trial of lenalidomide maintenance for treated MM patients who have stable or responsive disease.
- After screening, eligibility determination, and enrollment; subjects will receive lenalidomide 10 mg by mouth daily on days 1-21 of repeated 28-day cycles. When necessary, lenalidomide will be held and restarted in accordance with accepted clinical dose modification guidelines.
- Subjects may continue lenalidomide until disease progression, unacceptable toxicity or completion of two years of lenalidomide therapy and the 30 day safety follow-up visit.
- Blood will be obtained to assess changes in T cell (CD4, CD8), NKT and NK cell numbers by flow-cytometric analysis at pre-specified time points during lenalidomide maintenance.
- Blood samples and/or bone marrow samples where possible, will be used for additional research studies, which may include functional analyses of immune-cell subsets, analyses for cytokines, chemokines, antibodies, tumor cell antigen targets, and/or other markers.

TABLE OF CONTENTS

Précis.....	3
Table of Contents.....	4
1 INTRODUCTION	6
1.1 Study Objectives	6
1.2 Background and Rationale	6
2 ELIGIBILITY ASSESSMENT AND ENROLLMENT.....	11
2.1 Eligibility Criteria	11
2.2 Screening Evaluation.....	13
2.3 Registration Procedures.....	14
2.4 Baseline Evaluation.....	15
3 STUDY IMPLEMENTATION	15
3.1 Study Design	15
3.2 Drug Administration	15
3.3 Dose Modifications	16
3.4 Study Calendar	20
3.5 Criteria for Removal from Protocol Therapy and Off Study Criteria	22
4 CONCOMITANT MEDICATIONS/MEASURES	23
4.1 Tumor lysis syndrome.....	23
4.2 Bone Disease/Extramedullary Disease.....	23
4.3 Use of steroids	23
4.4 Hypercalcemia.....	23

1 INTRODUCTION

1.1 STUDY OBJECTIVES

1.1.1 Primary Objective:

- Assess T cell (CD4, CD8), NKT and NK cell numbers in peripheral blood of MM patients during the course of lenalidomide maintenance therapy.

1.1.2 Secondary Objectives:

- Determine progression free survival
- Determine duration of response
- Assess NK cell function and activity
- Assess changes in B cell subsets, myeloid derived suppressor cells and T regulatory cells by phenotypic analysis during the course of therapy
- Assess expression of CRBN, and how it relates to NK cell number and activity

1.2 BACKGROUND AND RATIONALE

Multiple myeloma overview

Multiple myeloma (MM) accounts for 1% of all cancers and approximately 10% of all hematologic malignancies [1]. It is defined as a clonal proliferation of malignant plasma cells in the bone marrow, with the presence of a monoclonal protein in serum or urine and with features of end-organ damage including hypercalcemia, renal insufficiency, anemia, and bone lytic lesions [2]. Almost all patients evolve from an asymptomatic premalignant state termed monoclonal gammopathy of undetermined significance (MGUS) [3]. MM is incurable with an estimated median survival of 6-7 years in standard risk myeloma and 2-3 years in high risk disease despite treatment with autologous stem cell transplantation (ASCT) [4].

Maintenance therapy in MM

Maintenance therapy to achieve sustained suppression of residual disease following chemotherapy induction or ASCT has long been viewed as a desirable approach for extending survival in MM. Even the most intensive therapy followed by ASCT is usually unable to extend progression-free survival (PFS) to beyond 36 months, with the majority of patients eventually experiencing relapse. Efforts to establish long-term maintenance regimens using alkylating agents, interferons, and corticosteroids have been hindered by unacceptable toxicity and have largely failed to improve survival [5]. One study in which patients were randomized to receive either prednisone 50mg or 10mg per day showed an overall survival (OS) benefit in the 50mg arm of 37 v. 26 months, $P=0.05$ [6]. However, these results have not been confirmed in a subsequent controlled clinical trial, and patients treated with corticosteroid maintenance are less responsive to these agents at relapse [7]. Increased survival in MM has been achieved with the introduction of novel therapeutic agents including the immunomodulatory drug lenalidomide (Revlimid; Celgene) [8].

[figure not shown]
Investigational drug lenalidomide

Abbreviated Title: Revlimid maintenance for MM

Version Date: 01/06/2017

REVLIMID® (lenalidomide), a thalidomide analogue, is an immunomodulatory agent with anti-angiogenic properties. The chemical name is 3-(4-amino-1-oxo 1,3-dihydro -2H-isoindol-2-yl) piperidine-2,6-dione and it has the following chemical structure:

Chemical Structure of Lenalidomide

Lenalidomide possesses diverse tumoricidal and immunomodulatory properties and a favorable toxicity profile. Lenalidomide overcomes many of the issues associated with long-term thalidomide therapy, especially neuropathy. Lenalidomide in combination with dexamethasone received FDA approval after two parallel studies demonstrated response rates of 61% for lenalidomide plus dexamethasone versus 22% for dexamethasone alone in patients with relapsed/refractory multiple myeloma [9]. The drug has also been studied in newly diagnosed patients in combination with low-dose dexamethasone, as well as with bortezomib and dexamethasone.

Lenalidomide role as maintenance therapy

A pilot phase 2 study showing the feasibility and efficacy of lenalidomide consolidation and maintenance therapy laid the basis for further clinical testing of lenalidomide. Recently, three large phase III trials comparing lenalidomide maintenance to placebo found significant progression-free survival (PFS) benefit for both ASCT-eligible [10, 11] and ineligible [12] patients. Additionally, one study [11] reported a significant difference in 3 year OS between the lenalidomide and placebo arms, 88% v. 80%, p=0.03. In all three studies [10-12], the progression-free survival benefit of lenalidomide was independent of the response to induction therapy at randomization, age, disease stage, β 2-microglobulin level, use or nonuse of lenalidomide or thalidomide induction therapy, and presence or absence of cytogenetic abnormalities (though cytogenetic data were available only in the study by Attal et al. [10] and only in a few patients).

These findings are summarized in table 1.

Abbreviated Title: Revlimid maintenance for MM

Version Date: 01/06/2017

Table1: Lenalidomide maintenance studies after ASCT and conventional chemotherapy

Study	Induction	No.	Maintenance	PFS/TTP (median)	OS	Discontinue due to AE
IFM 2005-02 [10]	VAD/other→ Single or double ASCT → Len. consolidation x 2 cycles	a. 307	a. Len. 10 mg /d with dose adaptations (5-15 mg/d)	a. 41 mo	a. 73% (4 y OS)	a. 27%
		b. 307	b. Placebo	b. 21 mo p <0.001 HR 0.50	b. 75% p = 0.70 HR 1.06	b.15%
CALGB 100104 [11]	Any → ASCT	a. 231	a. Len. 10-15 mg/d	a. 46 mo (TTP)	a.88%) (3 y OS)	a. 12%
		b. 229	b. Placebo	b. 27mo p <0.001	b. 80% p= 0.03	b. 2%
MM 015 [12]	a. Mel. + Pred. + Len.	a. 152	a. Len. 10 mg/d, days 1-21	a. 31 mo	a. 70% (3 y OS)	a. 20%
	b. Mel. + Pred. + Len.	b. 153	b. Placebo	b. 14 mo	b. 62%	b. 16%
	c. Mel. + Pred.	c. 154	c. Placebo	c. 13 mo p <0.001	c. 66% p =0.254	c. 2.9%

PFS- progression free survival; TTP- time to progression; OS- overall survival; SPM- second primary malignancies; VAD- vincristine, adrimycin, dexamethasone; ASCT- autologous stem cell transplant; Mel.-melphalan; Pred.-prednisone; Len.- lenalidomide; AE - adverse events

Lenalidomide maintenance therapy was well tolerated with expected and manageable side effects including mild hematotoxicity and infections. There was no increase in neurotoxicity or thromboembolic complications. Most patients were able to continue maintenance treatment without the need to discontinue therapy because of adverse events. Of note, there was a 7 to 8% rate of second primary cancers in the lenalidomide groups as compared with 3 to 4% in the placebo groups. This increase in second cancers led to discontinuation of lenalidomide in the trial reported by Attal et al [10]. Post hoc analysis with second cancers scored as events showed a median event-free survival of 40 to 43 months versus 23 to 27 months in both transplantation trials [10, 11] and 29 months versus 13 months in the trial that compared MPR-R with placebo [12], providing support for a magnitude of benefit associated with lenalidomide that seems to outweigh the risk of second cancers. The development of second primary cancers may also be due in part to other factors, some of which include prior use of various MM drugs with known leukemogenic potential, MM-related disease factors, host-related factors, as well as environmental and behavioral factors [13]. Further studies are needed to evaluate the true risk of this complication, to identify risk factors for its development, and hopefully, to develop strategies for the prevention of second primary cancers. Before more information is available, physicians and patients must weigh the benefits of lenalidomide maintenance therapy against the low but relevant risk of second cancers.

Lenalidomide mechanism of action

The mechanism of action of lenalidomide remains to be fully characterized. Although the exact mechanisms of lenalidomide's action are unknown, a number of mechanisms are postulated to be responsible for lenalidomide's ability to provide disease control. The anti-MM effect of lenalidomide is thought to be mediated by the combined effects of activation of immune effector cells (both T and NK cells), tumor down regulation of critical pro-survival cytokines (including

Abbreviated Title: Revlimid maintenance for MM

Version Date: 01/06/2017

IL-6, TNF- α , PDGF and VEGF), direct inhibition of plasma cell proliferation, and suppression of angiogenesis [14, 15, 16].

Lenalidomide effect on NK, NKT, and T cells

Data suggest that part of the therapeutic efficacy of lenalidomide may be via the promotion of NK cell-mediated responses against MM cells. A number of studies and our unpublished preclinical work from (table 2) has demonstrated that as the disease progresses to advanced states from MGUS to MM, there is an associated decline in the NK cell number, and associated anti-MM activity[17, 18, 19].

Table 2: Data from natural history study 10-c-0096 comparing NK cell numbers in subjects with monoclonal gammopathy of uncertain significance and smoldering multiple myeloma

Disease	N	Variable	Mean (k/ μ L)	p-value
MGUS	33	WBCs	6.41	0.03
SMM	37		5.32	
MGUS	33	NK cells	0.89	0.07
SMM	37		0.69	
Mayo Clinic SMM Risk Score 1	17	NK cells	0.85	0.004
Mayo Clinic SMM Risk Score 2	18		0.53	

MGUS- monoclonal gammopathy of undetermined significance; SMM- smoldering multiple myeloma

Lenalidomide can augment NK cell number, cytotoxicity and NK cell–driven antibody-dependent cell-mediated cytotoxicity (ADCC) in several ways [14]. In vitro studies have shown that peripheral blood mononuclear cells (PBMCs) are required for lenalidomide-induced NK cell function, and this is achieved indirectly through activation of nuclear factor of activated T cell 2 (NFAT2) in T cells [20, 21]. In this way, lenalidomide activates T cells to produce IL-2, which in turn stimulates NK cell activation and function against MM [20]. Lenalidomide causes enhancement of antigen-specific CD8+ T-cell cytotoxicity, upregulation of Fc-gamma receptor signaling leading to increased NK cell activity, and activation of NKT cells [14]. Lenalidomide has been shown to increase CD16 expression on NK cells and facilitate ADCC against MM [22]. Lenalidomide can also down-modulate suppressor of cytokine signaling (SOCS) 1 expression in NK cells, resulting in a higher sensitivity to activating stimuli in the microenvironment [23]. Finally, lenalidomide also appears to favorably modulate the balance of NK cell activating and inhibitory ligand expression on MM targets. This action of lenalidomide may be of particular interest as initiation of a cytotoxic response by an NK cell is mediated through balance of signals obtained through inhibitory receptors such as killer immunoglobulin-like receptors (KIRs) and CD94–NKG2A [24], and activating receptors including NKG2D, DNAM-1, and Nkp46 [24]. Lenalidomide up regulates expression of ULBP-1 on MM cells and decreases expression of PD-L1, which both result in improved NK cell surveillance, recognition and lysis of MM tumor targets [26, 27]. Changes in NK cell receptor ligand expression on MM cells and, hence, their resistance to NK cell–mediated killing may underlie the development of more proliferative and refractory plasma cell clones as MM progresses [28, 29] and treatment with lenalidomide in maintenance setting may provide a means to promote NK cell–mediated control over MM .

Furthermore, prior smaller investigations in relapsed multiple myeloma have reported lenalidomide to increase the numbers of T cells (CD4, CD8), NKT and NK cells patients [30, 31]. Similar findings have been reported in studies based on myeloma cell lines [32, 33]. In a recent study lenalidomide was found to be particularly active in patients with higher cereblon (CRBN) expression, suggesting CRBN plays a role in lenalidomide-mediated immune activation [34]; however, the relationship between these observations and a clinical benefit is unclear.

Lenalidomide in combination with dexamethasone has been FDA-approved to treat relapsed and refractory MM. Interestingly, however, in the setting of a clinical trial of lenalidomide and dexamethasone, correlative studies demonstrated that while NK cell number was increased from a mean of $2.20 \pm 0.05 \times 10^5/\text{mL}$ (baseline) to a mean of $3.90 \pm 0.03 \times 10^5/\text{mL}$ (cycle 6; $P = .05$), cytotoxicity was irreversibly reduced from $48.9\% \pm 6.8\%$ to $27.6\% \pm 5.1\%$ ($P = .0028$), attributed mainly to blunting of lenalidomide's immunostimulatory effects on patient NK cells by concurrent dexamethasone administration [35]. Hence, single-agent lenalidomide seems to be the logical choice for maintenance treatment when tumor load has already been reduced significantly and control of the residual tumor cells by active immune surveillance is the clinically relevant priority. Given the presumed broad immune stimulatory effects of lenalidomide, it may be of clinical and scientific importance to investigate changes in immune cells in the setting of extended dosing (i.e. maintenance therapy) with this agent. Currently, there is no information available on this topic.

Lenalidomide effect on B cell subsets, MDSC and T regulatory cells

Regulatory T cells (Tregs) and myeloid-derived suppressor cells (MDSCs) have been shown to inhibit the activation and function of T cells that participate in antigen-specific immune responses. Tregs are potent immunosuppressive cells of the immune system that promote progression of cancer through their ability to limit antitumor immunity and promote angiogenesis. Higher proportions of Tregs have been reported in the PBMCs of patients with several types of tumors [36, 37, 38] including MM [39, 40]. Lenalidomide has been shown to inhibit the proliferation of FOXP3⁺ CTLA-4⁺CD4⁺CD25^{high} Tregs in vitro [41]. In humans, MDSCs are defined as CD14-CD11b⁺ or cells that express the myeloid marker CD33 and lack markers for mature myeloid and lymphoid cells in combination with low expression of HLA-DR [42]. Recently, new populations of CD14⁺HLA-DR^{-/low} MDSCs have been identified in patients with hepatocellular carcinoma [43] and MM [44]. MDSCs accumulate as a consequence of factors associated with inflammation, such as increased secretion of vascular endothelial growth factor (VEGF), GM-CSF, IL-1 β , IL-6 and PGE2, factors that are also elevated in patients with MM [45]. These changes in Treg and MDSC populations have not been characterized in the setting of lenalidomide maintenance in patients with MM. Cytokines and growth factors directly regulate proliferation, differentiation and death of normal B-lymphocytes, and abnormal cytokine networks clearly exist within the MM microenvironment. A recent in vitro study showed that lenalidomide significantly suppresses immunoglobulin synthesis by B cells [45], but we have limited knowledge of lenalidomide's effect on B cell populations in patients receiving maintenance therapy.

To conduct a comprehensive evaluation of a range of immune cells in relation to lenalidomide maintenance therapy, we will include analyses of B-, T-, NK and NKT cells and important signaling cytokines.

Proposed Study Investigation with Biomarker Studies

The primary objective of this study is a longitudinal assessment of T cell (CD4, CD8), NKT and NK cell populations during the course of lenalidomide maintenance therapy in patients with MM. Peripheral blood samples from all enrolled patients will be collected and batched for biomarker analysis at baseline, after cycles 1, 3, and 6, and then after every 6 cycles while receiving lenalidomide therapy, until completion of the study. The assays will be run on the batched samples for first ten patients at baseline, after cycles 1, 3, and 6 to determine the appropriate time points of assays for the subsequent patients. Samples will also be collected from all patients at the time of disease progression. Blood samples and bone marrow samples will be used for additional research studies, which may include functional analyses of immune-cell subsets, analyses for cytokines, chemokines, antibodies, tumor cell antigen targets, and/or other markers. Effective with Amendment D, bone marrow aspirate and biopsy will be obtained for research studies at the discretion of the PI. Patients' tumor cells, where possible, will be characterized by gene expression profiling to enhance our understanding of lenalidomide efficacy and safety in a genetically diverse tumor population.

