3 STUDY IMPLEMENTATION

3.1 STUDY DESIGN

- Patients with newly diagnosed or relapsed MM with stable disease or better clinical response after induction or re-induction treatment will be enrolled on this phase II study and treated with a maintenance dose of lenalidomide 10 mg daily on days 1 to 21 of repeated 28-day cycles.
- Patients who complete at least 3 cycles will be evaluable for primary endpoints. Patients who do not complete three cycles of therapy will not be included in the analysis of primary or non-primary endpoints; and will be replaced by new patients.
- Using flow cytometry on peripheral blood, the four primary outcomes of T cell (CD4, CD8), NKT and NK cell numbers will be measured at pre-specified treatment time points to determine the difference in the counts of these parameters for each patient.

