5 BIOSPECIMEN COLLECTION

5.1 BIOMARKER STUDIES FOR RESEARCH

1) Blood/Urine

Sampling Time Points for biomarker studies/ biospecimen banking

	Baseline	C 2 D1 (within 3 days prior)	C 4 D1 (within 3 days prior)	C 7 D1 (within 3 days prior)	Every 3 cycles starting at cycle 7 D1 (within 3 days prior)	Every 6 cycles starting at cycle 7 D1 (within 3 days prior)	Disease progression	At CR
Blood for biomarker analysis	x	x	x	x		x	x	x
Bone marrow*	x						x	x
Blood/Urine Biopspecimen storage bank	x	x	x	x	x		x	x

- Blood samples for biomarker studies will be collected from all patients at baseline, after cycles 1, 3, and 6, and then after every 6 cycles while receiving lenalidomide therapy, until completion of the study. The samples will be batched for later analysis.
- The assays will be run on the batched samples for first ten patients at baseline, and after cycles 1, 3, and 6 to determine the appropriate time points of assays for the subsequent patients.
- Blood and urine specimens will be collected from all patients who agree to participate in optional studies and stored for establishing biospecimen storage bank. These specimens will be collected at baseline, after cycles 1, 3, and 6 and after every three cycles while receiving lenalidomide. Specimens will also be collected and stored at the time of documented CR and disease progression. IRB approval will be obtained before using any samples to conduct studies that are not described within this protocol.

Abbreviated Title: Revlimid maintenance for MM

Version Date: 01/06/2017

- d. Collection and storage of peripheral blood and urine for biospecimen storage bank is outlined in appendix C.
- e. Processing of peripheral blood for biomarker studies is outlined in appendix D.
- f. At any given time, up to 100cc of peripheral blood will be collected. The amount of blood collected will be dictated by the number of experiments to be performed, and by the patient's peripheral blood count.
- g. The standard number of peripheral blood tubes drawn for storage at each of the above time points may include but are not limited to the following: one 7-8 mL serum tube, one 7-8 mL plasma heparinized tube, and one 7-8 mL EDTA tube.
- h. The standard number of peripheral blood tubes drawn for biomarker analysis at each of the above time points may include but are not limited to the following: two 7-8 mL plasma heparinized tubes.

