8 STATISTICAL CONSIDERATIONS

8.1 STUDY DESIGN/PRIMARY ENDPOINTS

This is a single arm, single stage, phase II trial to evaluate maintenance therapy with the immunomodulatory agent lenalidomide in treated MM patients who have stable or responsive disease. After screening, eligibility determination, and enrollment; subjects will receive lenalidomide 10 mg by mouth daily on days 1-21 of a 28-day cycle. Subjects may continue lenalidomide until disease progression, diagnosis of new malignancy, unacceptable toxicity, investigator discretion, or voluntary withdrawal. When necessary, lenalidomide will be held and restarted in accordance with accepted clinical dose modification strategies.

The primary objective of this study is a longitudinal assessment of T cell (CD4, CD8), NKT and NK cell populations during the course of lenalidomide maintenance therapy in patients with MM. Using flow cytometry on peripheral blood obtained at baselines and after 3 cycles of therapy, we will determine the primary measures at both time points. Comparisons at other time points will be considered exploratory..

With 28 patients enrolled, we will have 80% power to detect an effect equal to 0.67 SD of the difference in counts (0.67 SD effect size) of T cells (CD4, CD8), NKT and NK cells with a two-tailed paired t-test and a significance level of 0.013 for each test. Thus, using a strict Bonferroni adjustment, we would have an overall significance level of 0.05 for the four tests. In practice, a less overly conservative Hochberg adjustment may be used instead of a Bonferroni adjustment. In addition, if the difference in the numbers of any type of cells is not normally distributed ($p < 0.05$ by a Shapiro- Wilks test), then a Wilcoxon signed rank test will be performed instead.

Results will be presented in a descriptive format.

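### The first-ten assay rule in sections 1.2 and 5.1 does not exempt the baseline and after-cycle-3 assays that the primary test in 8.1 needs from all 28 patients (minor wording fix)

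*Combined protocol and SAP*

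**What the plan says.** **The assay rule.** Sections 1.2 and 5.1 have biomarker blood collected from every patient at baseline, after cycles 1, 3 and 6, and every six cycles after that, and batched. Section 5.1 continues: "The assays will be run on the batched samples for first ten patients at baseline, and after cycles 1, 3, and 6". Both sections give the purpose: "to determine the appropriate time points of assays for the subsequent patients". No time point is set aside as fixed.

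**The primary analysis.** Section 8.1 says that from "peripheral blood obtained at baselines and after 3 cycles of therapy, we will determine the primary measures at both time points", and adds: "Comparisons at other time points will be considered exploratory". On size it says: "With 28 patients enrolled, we will have 80% power to detect an effect equal to 0.67 SD", "with a two-tailed paired t-test and a significance level of 0.013 for each test". It describes the four tests together as holding an overall level of 0.05 under Bonferroni in its strict form, with Hochberg as a possible alternative. It does not mention the first-ten rule.

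**Measurement and evaluability.** Section 3.1 says "the four primary outcomes of T cell (CD4, CD8), NKT and NK cell numbers will be measured at pre-specified treatment time points", without naming those points. It also says: "Patients who complete at least 3 cycles will be evaluable for primary endpoints". Patients who stop before completing three cycles are replaced.

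**The concern.** Two rules bear on the same samples. One fixes baseline and after-cycle-3 as the primary pair. The other lists those two points among the ones whose later use depends on what the first ten patients show. Nothing in the documents says which rule prevails.

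The four paired tests are the only analysis in section 8 with a power statement, and a pair exists only if both samples are assayed. The replacement rule in 3.1 does not guard against this gap, because it depends on cycles completed and not on assays run. A patient who completes three cycles but whose Cycle 4 Day 1 sample is left unassayed stays evaluable, is not replaced, and contributes no pair. There is also a question of principle: observed after-cycle-3 results should not influence whether later after-cycle-3 assays are run when that comparison is the fixed primary test.

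**Working it through.** **Inputs.** From section 8.1: n = 28, effect d = 0.67 SD of the paired differences, two-sided paired t-test, per-test level 0.013, four tests, stated power 80%. From sections 1.2 and 5.1: ten patients in the first review, leaving 28 - 10 = 18 later patients. From section 8.2: 2 to 3 enrolments per month.

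**Formula.** Power = P(|T| > t_crit), where T is noncentral t with n - 1 degrees of freedom and noncentrality d x sqrt(n), and t_crit is the 1 - alpha/2 quantile of the central t.

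**The plan's own figure.** For n = 28 the noncentrality is 0.67 x sqrt(28) = 3.55. Power is 80.4% at 0.013, so the stated 80% reproduces. The smallest n that reaches 80% at 0.013 is 28. A normal approximation gives 85.6% and a one-sided test 87.6%, so the exact two-sided paired t is evidently the method used.

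**Fewer assayed pairs (d = 0.67, level 0.013).**

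| Pairs | Power |
|---|---|
| 28 | 80.4% |
| 27 | 78.5% |
| 24 | 71.8% |
| 20 | 60.6% |
| 15 | 43.2% |
| 10 | 23.8% |

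The effect detectable with 80% power is 0.67 SD with 28 pairs and 1.28 SD with 10.

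**Per-test level.** 4 x 0.013 = 0.052, whereas 4 x 0.0125 = 0.050. At 0.0125, power with 28 pairs is 79.97%, or 80.0% after rounding. With 10 pairs it is 23.2%.

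**Timing.** Assume treatment starts at enrolment and 28-day cycles run without delay. Six cycles take 168 days, about 5.52 months; three take half that, 2.76 months.

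- At 2 per month, the tenth patient enrols at month 5.0 and completes cycle 6 at 5.0 + 5.52 = month 10.5. By then 2 x 10.5 = 21 patients are enrolled, and about 15 have passed cycle 3.
- At 3 per month, the tenth patient enrols at month 3.3 and completes cycle 6 at month 8.9. By then about 26 are enrolled, and about 18 have passed cycle 3.

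So by the time the first-ten results could be complete, more than half of the after-cycle-3 samples would already be stored. The rule would largely decide which stored samples are assayed, not which are drawn.

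**The case against.** The case on the other side is strong.

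- **Section 8.1 is unconditional.** It is the only place that defines the primary test, and it labels every other time point exploratory. With 3.1 (pre-specified points, three-cycle evaluability, replacement), the documents harmonise easily: the first-ten review tunes the exploratory schedule. Replacing patients who fall short of three cycles would serve little purpose if later after-cycle-3 samples need not be assayed.
- **The literal reading proves too much.** The rule lists baseline too. Taken at its word, it would let baseline be dropped, leaving no change to measure.
- **The assays in question are not defined.** Section 5.2 describes many, including proliferation, NK cytotoxicity, Treg and MDSC panels, and cytokines. The rule may not be aimed at the four primary counts at all.
- **Samples are kept.** Section 3.4 (footnote i) and section 5.1 collect Cycle 4 Day 1 blood from everyone, and Appendix D puts the cells in liquid nitrogen. A skipped assay is recoverable.

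All of this stands as evidence of intent, and it rules out a stronger reading that a reader might infer: that the trial will end with ten pairs and 24% power. Reaching that figure requires overriding 8.1, dropping after-cycle-3 for all 18 later patients, never running their stored samples, and having all ten first patients evaluable. The documents support none of these steps.

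The objection does not supply the missing sentence. The rule is printed twice without limit, directly after the primary objective in 1.2. Collecting and storing a sample does not require that it be assayed.

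**Conclusion.** The concern holds as a minor conflict of wording that touches the primary endpoint. Under the natural reading there are 28 pairs, power is as stated, and nothing is lost. Under the rule as written, some primary assays could be omitted because of observed results. Even one omission takes power below target (27 pairs, 78.5%), and four take it to 72%. The 24% figure is an outer bound, not an expectation. These figures assume the plan's own effect of 0.67 SD, its exact paired t-test, and one pair per evaluable patient.

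The documents show no data actually lost and no error in the stated power. They also do not show whether the first-ten review is still to come: this version is dated 01/06/2017 and section 3.5.2 refers to an amendment of February 2015.

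The per-test level is a separate and smaller matter. The printed 0.013 looks like 0.0125 rounded, and as printed it sums to 0.052. A reader might infer that the error rate is materially inflated. It is not: the excess over 0.05 is at most 0.002, and for independent tests the overall rate would be 1 - (1 - 0.013)^4 = 0.051.

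**What to change.** In sections 1.2 and 5.1, after the first-ten sentence, add: *Baseline and Cycle 4 Day 1 (after cycle 3) samples are assayed for the four primary counts in all evaluable patients, whatever the first-ten results. The first-ten review may change only the exploratory time points.* If the review has already taken place, confirm that the stored baseline and Cycle 4 Day 1 samples of later patients have been, or will be, assayed.

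In section 8.1, replace 0.013 with 0.0125. Power with 28 pairs moves from 80.4% to 80.0%, so the stated 80% still stands after rounding.

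The cost is a short addition in two places and one corrected figure. No extra blood draw or patient is needed, because the samples are already collected from everyone. What is given up is the freedom to skip primary-count assays at the two primary time points, at most 18 of them after cycle 3. The first-ten review keeps its use for the exploratory schedule.
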